4.2 Project Outcomes

Primary Endpoint:

- Correlation of sonographic estimated gastric volume with volume aspirated through a naso- or oro-gastric tube, that was placed by routine.

Secondary Endpoints:

- Performance over time, improvement of examination technique, critical number of examinations to achieve a high quality standard (>80% congruence for estimated and aspirated gastric volume in fluids).
- Association of performance with experience, residents vs. attendings.
- Number of patients classified as empty -> possible implications for management and induction.
- Number of patients with full stomach -> possible implications for management and induction.
- Time used for examinations, time used with growing experience.
- Estimated aspiration risk vs. sonographic gastric volume.
- Total number of pulmonary aspirations.

5 Project Description

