This model is based on gastroscopic fluid assessment and highly validated by several publications. ²⁸

After placement of the routine naso- or orogastric tube, which is a standard procedure for both RSIs and advanced laryngeal masks at our institution - we compare the calculated and effective suctioned volume of the gastric content and analyse the difference and quality of the sonographic measurement. In some patients a gastric tube is contraindicated or not possible to place correctly. In this case an exclusion of the study is mandatory according to our exclusion criteria. Patients planned for an intervention in a regional anaesthesia will not receive a gastric tube.

In exceptional cases the responsible anaesthesiologist is allowed to upgrade patients from an advanced laryngeal mask to an RSI after ultrasound performance to ensure patient safety. Downgrading from RSI to advanced laryngeal masks on base of the ultrasound results is not allowed.

All data concerning the sonography will be noted in a password protected Excel sheet only available to institute members by the responsible anaesthesiologist performing the examination. Background patient data including demographic data are collected during the structured preoperative anaesthesiologic assessment according to in house standard procedures and data management. Data will be coded and condensed in a password-protected Excel File, only accessible to study personnel. A patient identification log will be kept in a locked archive for data verification processes only. To guarantee seamless traceability we will create a immutable PDF file after all relevant changes or at least once per month and store it in a separate study folder only accessible to study personnel. An additional hard copy will be created and printed once per month and stored in a locker in our administrative office.

9 Safety

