11.1 Determination of Sample Size

Within a study period of 6 to 12 months, all elective and emergency patients scheduled for a Rapid Sequence Induction (RSI) will be included in this study. In 2019, a total of 2'718 general anaesthesias with Rapid Sequence Inductions (RSI) were undertaken at our institution. 275 thereof were children < 18 years of age. Further, 204 Rapid Sequence Inductions were performed in life threatening situations (category: Notfall <1h, vital, sofortiger Eingriff notwendig by the Swiss Society for Anaesthesiology and Resuscitation, A-QUA) where a delay is medically and ethically not acceptable. Further, we estimate that a number of 1000 patients per annum have one or more aspiration risk factors, receiving an advanced laryngeal mask or a regional anaesthesia. In conclusion, we aim to include at least 1500 up to 3200 patients in a one year recruitment period. On basis of the publication of Arzola et al.³⁶ individual differences in sonography performance can already be detected after 30 to 40 examinations. Although our residents will already have performed at least as many examinations before first patient inclusion, we postulate, that a similar number of patients per capita will be needed to investigate interindividual performance. Given an estimated number of 30 residents and 20 attendings participating, we aim to include 1500 - 2000 patients.

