11.2 Statistical Methods

Primary Endpoint:

- Correlation of sonographic estimated gastric volume with volume aspirated through a naso- or orogastric tube.

Secondary Endpoints:

- Performance over time (improvement of examination technique, critical number of examinations).
- Association of performance with experience, residents vs. attendings.
- Number of patients classified as empty -> possible implications for management and induction.
- Number of patients with full stomach -> possible implications for management and induction.
- Time used for examinations, time used with growing experience.
- estimated aspiration risk vs. sonographic gastric volume.
- Total number of pulmonary aspirations.

Collected Variables:

- Patient Demographic: Age, sex, gender, height, weight, BMI, ASA Classification, patient history, concomitant medication, concomitant disease, intervention performed, anaesthetic risk class of the intervention, surgical department of the intervention, urgency of the intervention.
- Sonographer Demographic: education level, years of anaesthesiologic experience, years of sonographic experience.
- RSI Indication.
- Last meal/ drink before surgery.
- Subjective estimated aspiration risk (graded by the responsible anaesthetist).
- Sonography quality, reasons for poor quality.

- Sonographic quality of gastric content.
- Sonographic quantity of gastric content.
- Time for examination.
- Effective quantity of gastric content.
- Theoretical change in anaesthesiologic management.
- Reason for not performing gastric sonography.

Analysis:

- Demographic Analysis.
- Institution overall success analysis.
- Interpersonal success analysis with logistic regression and cumulative sum learning curves.
- Analysis of possible changes in anaesthesiologic management.

12 Ethics

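### Protocol 11.2 names logistic regression with no examiner effect; if it is fitted in ordinary form to residents vs attendings, the intervals are too narrow

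*Protocol*

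**What the plan says.** Among the analyses in section 11.2, one line names statistical models: "Interpersonal success analysis with logistic regression and cumulative sum learning curves". It gives no outcome definition, covariates, examiner term or variance estimator. Logistic regression is the only regression model in the protocol.

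The secondary endpoints in the same section include "Association of performance with experience, residents vs. attendings". No model is tied to that endpoint explicitly.

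Section 11.1 sets out the structure of the data. It relies on a published learning-curve study for the statement that "individual differences in sonography performance can already be detected after 30 to 40 examinations", postulates that "a similar number of patients per capita will be needed to investigate interindividual performance", and concludes: "Given an estimated number of 30 residents and 20 attendings participating, we aim to include 1500 - 2000 patients".

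Two other places limit how many scans per examiner can be scored. The quality standard in section 4.2 is a "critical number of examinations to achieve a high quality standard (>80% congruence for estimated and aspirated gastric volume in fluids", so it applies to fluid content only. Section 8.1 adds: "Patients planned for an intervention in a regional anaesthesia will not receive a gastric tube".

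**The concern.** The sample size rests on repeated scans by the same people and on the expectation that those people perform differently. Scans by one examiner should then resemble each other more than scans by different examiners. The regression named one section later does not, in its ordinary form, allow for that.

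This matters most for covariates that are fixed, or nearly fixed, within an examiner: resident or attending status, and years of experience. For these the evidence comes from about 50 people, not from 1500 or more scans. An unclustered model would give standard errors that are too small and a p-value that overstates the evidence. Validating the training is the study's stated aim, and identifying confounders and variables in individual training is a secondary objective. A spurious gap between residents and attendings would feed directly into what the report says about who performs well after the training.

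**Working it through.** **Inputs from the protocol (11.1).** 30 residents and 20 attendings, and 30 to 40 examinations each.

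**The plan's own figure.** (30 + 20) × 30 = 1500 and (30 + 20) × 40 = 2000. This reproduces the stated target exactly, so the target is a number of examiners times a number of scans per examiner. The protocol gives no power, effect size or intraclass correlation for this comparison.

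**Assumptions (not in the protocol).** Overall success rate 80%; no true difference between residents and attendings; an equal number m of scored scans per examiner; a normally distributed examiner effect on the logit scale; latent-scale intraclass correlation ρ of 0.01 to 0.20.

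**Formulas.**
- Examiner standard deviation on the logit scale: σ = √[ρ/(1 − ρ) × π²/3].
- Observed-scale correlation: ρ_obs = Var(p_i)/(0.80 × 0.20), where p_i is examiner i's success probability and the mean of p_i is held at 0.80.
- Design effect for a covariate constant within examiner: DE = 1 + (m − 1) × ρ_obs.
- Real rejection rate of a naive two-sided 5% test: 2 × [1 − Φ(1.96/√DE)].

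**Worked case, m = 30, ρ = 0.05.** σ = √(0.0526 × 3.290) = 0.416, which gives ρ_obs = 0.027. DE = 1 + 29 × 0.027 = 1.78 and √DE = 1.34. The rejection rate is 2 × [1 − Φ(1.96/1.335)] = 14%.

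**Range.** The simulated column is the naive log-odds-ratio test in 20,000 simulated studies of 30 against 20 examiners.

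| m | latent ρ | ρ_obs | DE | formula | simulated |
|---|---|---|---|---|---|
| 30 | 0.01 | 0.005 | 1.15 | 6.8% | 7.1% |
| 30 | 0.05 | 0.027 | 1.78 | 14.2% | 13.7% |
| 30 | 0.10 | 0.055 | 2.60 | 22.4% | 22.5% |
| 30 | 0.20 | 0.114 | 4.30 | 34.5% | 34.7% |
| 10 | 0.01 | 0.005 | 1.05 | 5.6% | 5.5% |
| 10 | 0.05 | 0.027 | 1.24 | 7.9% | 7.5% |
| 10 | 0.10 | 0.055 | 1.50 | 10.9% | 10.5% |
| 10 | 0.20 | 0.114 | 2.02 | 16.8% | 17.2% |

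With 40 scans per examiner the formula gives 7.4%, 17.1%, 26.9% and 40.1%. With ρ = 0 the naive test rejects in about 5% of simulated studies at every m. A comparison of examiner-level success proportions (Welch t test) stays between 4.8% and 5.5% throughout.

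**Why 10 scans is shown.** Volume congruence can be scored only when fluid is seen and a gastric tube is placed. Section 5.2 also allows a minimum of 500 patients, and 500/50 = 10 per examiner.

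**A note on scale.** The same number means more on the observed scale. An observed-scale correlation of 0.05 with m = 30 gives DE = 1 + 29 × 0.05 = 2.45, a correct standard error √2.45 = 1.57 times the naive one, and a rejection rate of 21%. It should not be read against the latent-scale row for 0.05.

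**The case against.** The strongest reply is that the protocol never says scans are independent. Logistic regression is a family name that can include a random examiner effect, generalized estimating equations, clustered standard errors or examiner as a factor, and a statistical analysis plan that is not at hand may settle the matter. The line in 11.2 is also labelled as a comparison between persons, and the residents vs attendings endpoint is listed separately with no model attached. All of this is correct, and it makes the point conditional. It does not remove it. The protocol names a model and omits the one feature that its own sample-size reasoning calls for. Entering examiner as ordinary fixed effects would not help, because the resident/attending contrast could then not be estimated separately.

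The size is also open to challenge. All examiners complete the same training and must be approved before their first patient, which may keep differences between them small. At a latent correlation of 0.01 the inflation is modest, and fewer scorable scans reduce it further. That stands, and it is why a range is given.

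A reader might infer more: that the conclusion on how much training is needed is invalid, or that the primary analysis is affected. The documents do not support either. The number of scans needed is a question within examiners, for which the same line names cumulative sum curves, and the calculation here covers only a covariate that is constant within an examiner. The primary endpoint, the correlation of estimated with aspirated volume, is a separate analysis.

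**Conclusion.** The point holds conditionally. The protocol plans data clustered by examiner, expects examiners to differ, and names a regression without saying how that clustering is handled. If the regression is fitted in ordinary form to residents vs attendings or to experience, its tests and intervals are anti-conservative at any positive intraclass correlation. With 30 scans per examiner the nominal 5% error becomes roughly 7% to 34% over latent correlations of 0.01 to 0.20; with 10 scorable scans it becomes roughly 6% to 17%.

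These figures rest on an assumed 80% success rate, equal numbers of scans per examiner and an intraclass correlation that the protocol does not supply. It would be wrong to say that the protocol has chosen to treat scans as independent; that is an inference from its silence. Only secondary endpoints are concerned. The change is worth making because it is cheap and the model as named leaves the error open.

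**What to change.** In section 11.2, replace the words logistic regression by mixed-effects logistic regression with a random intercept for examiner, and state that this model is used for resident/attending status and experience. Logistic regression with examiner-clustered standard errors is an acceptable alternative.

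The cost is a change of wording, slightly more analysis work, and wider but correct intervals. No extra patients and no new data field are needed, since learning curves for individual examiners already require each scan to be linked to its examiner. A random slope for scan number or a fixed list of case-mix covariates may be considered on other grounds, but neither is required to remove this problem.

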12.1 Independent Ethics Committee

Before this project will be conducted, the protocol, the proposed participant information and consent form as well as other project-specific documents will be submitted to a properly constituted Competent Ethics Committee (CEC), for formal approval. The decision of the CEC concerning the conduct of the project will be made in writing to the Sponsor-Project Leader before commencement of this project.

Significant changes to an authorised research project must be approved by the ethics committee before being implemented. Exempt from this requirement are measures which have to be taken immediately in order to protect the participants.

The following are considered to be significant changes:

- a. changes affecting the participants' safety and health, or their rights and obligations;
- b. a change of research site or conducting the research project at an additional site; or
- c. a change of the project leader or sponsor.

The Ethics Committee will be informed within 90 days regarding the termination or completion of the project.

12.2 Ethical Conduct of the Project

This project will be carried out in accordance with principles enunciated in the current version of the Declaration of Helsinki and Swiss regulatory authority's requirements.

12.3 Participant Information and Informed Consent

Prior to the project start each participant has to give their written informed consent after he/she was comprehensively informed - verbally and in writing - on the nature, relevance and impact of the project. The content of this information should be documented on the informed consent. Each participant must be informed that the participation in the project is voluntary and that he/she may withdraw from the project at any time and that withdrawal of consent will not affect his/her subsequent medical treatment. The participants will be given enough time to make their decision whether they would like to participate or not.

The consent to participate into the research project should be signed and dated by both, the participant and the project leader or a trained study person. A copy of the signed and dated subject information and informed consent form has to be handed out to the participant.

No project related procedures are to be conducted before a legally accepted written informed consent has been given.

13 Confidentiality and Data Protection

Data generation, transmission, archiving and analysis of health related personal data within this project; strictly follow the current Swiss legal requirements for data protection and according to the Ordinance HFV Art. 5. Prerequisite is the voluntary approval of the participant given by signing the informed consent prior start of participation of the research project.

Health related personal data captured during this project from participants are strictly confidential and disclosure to third parties is prohibited; coding will safeguard participants' confidentiality. Confidentiality will be ensured by using coded data. The code will be protected against unauthorized access and will be stored appropriately by the project leader. All patient related data will be destroyed after project termination.

The collected project data may be subject to inspection by the CEC.

14 Funding and Support

No external funding.

15 Compensation

Participants will not be compensated for their participation into this scientific research project.

16 Insurance

Insurance is covered by "Versicherung für klinische Versuche und nichtklinische Versuche" by Basler Versicherung AG (Policy no.: 30/4.093.845).

